Main Objective	Preliminary evaluation of an obstacle alerting system that may enhance user's independent mobility by improving their confidence to drive and their safety in driving a powered wheelchair.
Number of study centres	3
Number of participants	10 .
Inclusion Criteria	1. Adults who are not wheelchair users. 2. Willing and able to provide a valid consent. 3. Able to participate in interviews aided or unaided using preferred method of communication. 4. Willing to drive a powered chair. 5.
Exclusion Criteria	1. Lacks capacity to consent
Evaluation Criteria	Evaluation of obstacle alerting system by; 
• Adults who are not wheelchair users• Comparative analysis of driving patterns with and without the obstacle alerting system.• Analysis of driving patterns through smoothness movement, joystick deflection, positional mapping and daily usage. Searching for correlation between these patterns and user well-being, medication and location/environment.• Analysis of pre and post-trial interviews.
Participation duration	Typically up to 5 days
Duration of the study	9 months

2 Background

NOTE: Powered chair users will have underlying conditions which will make them more vulnerable to the impact of COVID-19. Therefore this revised protocol has been developed where adults who are not wheelchair users will carry out a preliminary evaluation of the Obstacle Alerting System.

2.1 Introduction

The goal of the project, “Empowerment of Disabled people through the User Coproduction of Assistive Technology” ([EDUCAT](#)), is to work with all stakeholders – including powered wheelchair users, carers, academics, healthcare professionals, user groups and industry - to develop an Assistive Powered Wheelchair. It is hoped that this Assistive Powered Wheelchair will include the following potential benefits to the user:

- Monitoring of changes in user wellbeing
- Monitoring the effect of medication
- Providing driving assistance to increase user confidence and safety in driving
- Enabling access to independent mobility for those not meeting current PWC prescription criteria

The EDUCAT project began with the development of a prototype driving assistance system [obstacle detection and avoidance] which was part of a three year European Union project, [SYSIASS](#)¹⁻⁷ by partners at the East Kent Hospitals University NHS Foundation Trust [EKHUFT], the University of Kent, University of Essex and ISEN University, Lille.

The goal of this prototype system was to improve the confidence and safety with which users can drive powered wheelchairs [PWC] by reducing the probability of collisions, especially when passing through doorways or down narrow corridors. The system achieved this by detecting the presence of obstacles and then modifying the PWC trajectory to avoid collision with those objects.

A further 12 month EU project, Empowerment of Disabled People through Ethics in Care and Technology [[EDECT](#)] then trialled this system with 12 PWC users recruited from the UK [REC reference: 14/EE/0164, Minor Amendment 2, Amendment date: 11 February 2015, IRAS project ID:141444], France, Belgium and the Netherlands. The system was further developed to include a prototype system to record and analyse the user’s joystick movements and to provide basic tactile/haptic feedback to alert the user that an obstacle is being approached and that the driving assistance system is beginning to modify the wheelchair trajectory.

The goal was to use pre and post-trial interviews to collect user specifications for the development of the PWC with Driving Assistance and their evaluation of their experience of driving the PWC with the collision avoidance system. These trials took place under carefully controlled conditions. The initial analysis of user joystick movement provided evidence to support the hypothesis that user state and driving confidence might be indicated by their individual driving patterns. The user feedback on the haptic feedback made it evident that a range of feedback options were required.

Building on the outcomes of these projects, the EDUCAT project has been funded for four years through the Interreg Va 2 Seas programme [10/2016 – 09/2020].

This project is broken down into three stages.

Stage 1: The goal of this stage was threefold.

Firstly to collect demographic information about the carers and users volunteering to take part in this stage.

Secondly questionnaires to obtain carer and user input to the criteria for the design and development of an assistive powered wheelchair.

Thirdly to further evaluate the hypothesis that the user’s driving patterns can provide diagnostic information about their condition and how confidently they are driving the powered chair.

To do this a recording system has been developed to collect data from;

- the powered chair data bus, including the user’s joystick movements.

- an inertial measurement unit (IMU)
- a Global Positioning Satellite (GPS) unit.

The IMU unit records acceleration, rate of turn and magnetic field. The data from the IMU will be used to identify any physical events e.g. collisions, passing over dropped kerbs etc. The GPS data will help to identify when the user is out of doors.

The hypothesis is being evaluated through analysis of the user's joystick movements, IMU and GPS data which will be correlated with the user's daily record of their perceived well-being, medication and the environments in which they are using the chair.

This stage is currently being run by East Kent Hospitals and Sussex Community NHS Foundation Trust [IRAS ID 235049].

Stage 2 Develop the Stage 1 system to include obstacle alerting. This system includes obstacle detection sensors e.g. infra-red, ultrasound and cameras, and a feedback system. The feedback system will have the options of auditory, haptic and visual information. This feedback will provide the user with information about the location and proximity of nearby objects. The hypothesis is that this information could help the user to drive more safely and confidently by being made aware of these objects.

The user is to evaluate this system.

Questionnaires will be used to collect user feedback before, during and after the each trial.

The anonymised data collected throughout the trial will be stored in local memory and also securely transmitted via the internet to the cloud.

The analysis of this data will be used to inform the on-going development of an obstacle alerting system which will help the user to drive more safely and confidently; thus enhancing the user's independent mobility and quality of life.

Stage 3: The Stage 2 system will be developed to use the information from the sensors to provide driving assistance by modifying the PWC trajectory to avoid collisions.

The efficacy of the system will be measured through analysis of the user's driving patterns, coupled with user interviews. This analysis will help to assess the effectiveness of this driving assistance system and provide feedback for the development of a user acceptable driving assistance system.

It is anticipated that the system developed by the end of Stage 3 will provide a basis for an assistive PWC that can be used for a range of tasks for PWC users including; improving user's access to independent powered mobility, monitoring changes in wellbeing and the effect of medication, monitoring progress during rehabilitation, training prospective users who may, with a driving assistance system, now be able to drive a PWC more safely and confidently.

The goal is to enhance the user's independent mobility and quality of life.

Because of the challenging nature of this project Ethics and HRA approval are being applied for stage by Stage.

Stage 1 is now underway [IRAS ID 235049].

This study protocol relates to **Stage 2** where, because of the impact of COVID-19, the participants will no longer be powered chair users but adults who are not wheelchair users.

As the project technology is developed it is planned to submit an application for Stage 3.

2.2 Object Alerting System (OAS)

In order to alert the user to the presence of objects three components are added to the Stage 1 Trial system.

- Object detecting sensors
- Feedback to the user about the location and proximity of those objects.

An Assistive Powered Wheelchair. Stage 2: Powered Wheelchair User Evaluation of an Obstacle Alerting System.

- Transmission of pseudonymised data to the project partner servers [The Cloud].

The system [Fig 1.] will consist of a Data Management Unit, using the propriety PWC data bus interface, a Communication and Control Unit [Android Tablet], Haptic feedback system, Reversing Camera and sensor nodes.

[figure not shown]

Figure 1: Obstacle Alerting System Block Diagram

[figure not shown]

Figure 2: Obstacle Alerting System Components

The sensors, control unit and display unit will be attached to the wheelchair in a manner which will not mark or damage the wheelchair or inadvertently affect wheelchair stability.

In this modified trial the research team's powered chairs will be used.

[figure not shown]

Figure 3: Example of a Powered Chair with Sensors and Display Units

2.2.1 The Data Management Unit

The Data Management Unit [DMU] collects data from the powered chair data bus and the sensors. It will also control the reversing camera and haptic feedback.

The Data Management Unit is connected to an Inertial Measurement Unit, a GPS unit, the proprietary Third Party Interface, the PWC data bus, the sensors and to the Communication and Control Unit.

The DMU can record:

- Time and date
- User Joystick Movements
- Powered Chair User profiles
- Whether actuators are being used
- Which controller is active – user or attendant
- GPS location – dependent on user consent
- Inertial Measurement Unit data
- Processed sensor data.

The DMU will transfer the data to the Communication Control Unit and display.

All data will be pseudonymised.

2.2.2 Powered Wheelchair Third Party Interface

In order to develop these systems it is necessary to safely extract data from the PWC data bus about the user's joystick activity and other control information made available by the manufacturer on the PWC.

[Dynamic Controls](#)¹⁰ have provided the bus interfaces for their DX and LiNX control systems. [Penny & Giles](#)¹¹ have made available the bus interface for their R-Net control system.

Dynamic and P&G estimate that they cover 95% of the powered chair control market worldwide.

2.2.3 Sensors and Data Recording

The sensors will be based on ultrasound, infrared, thermal and visible (camera) devices. The data from these sensors will be processed to provide the user with information about the location and proximity of objects close to the chair (within 2 metres).

The processing of any video data will ensure that it is not possible to identify any persons in the images, but only their presence and proximity.

The technology will be similar to that currently used to provide driving assistance in cars.

The sensor system also includes;

- **GPS Unit:** so that the location of the chair is known – whether outdoor or indoor. This information will help identify the impact of location on driving characteristics and of the efficacy of the OAS.
- **Inertial Measurement Unit:** The unit can be used to identify any physical events experienced by the chair. These events can be intended events e.g. climbing or descending kerbs, running over rough surfaces or potholes, docking against a bed. Or accidental events e.g. striking a door frame or wall. Data is to be analysed to try and identify signatures for these events.

2.2.4 The Communication and Control Unit

The Communication and Control Unit (CCU), a tablet computer, will process the data from the DMU and transmit pseudonymised data to the partners' secure server via the internet/mobile phone network.

The CCU also provides an interface to enable the:

- Researcher to configure the OAS before each trial
- Participant to configure feedback options
- Participant to enter data into questionnaires
- Participant to enter data into the Daily Diary throughout the trial
- Provision of Audio and visual feedback about object location and proximity (2.2.5).

2.2.5 Feedback to the Participant

The participant will be asked to evaluate a range of feedback options as follows:

Visual Feedback: Initially the participant will be provided with a display with minimal information to identify where objects are in relation to the wheelchair. Eventually a display with fuller data presentation, including an image of the surroundings and an indication of the proximity of that object, will be developed.

[figure not shown]

Figure 4: Visual Alert of Objects

Auditory Feedback: The participant will be provided with a range of options to evaluate. For example a basic beep with increasing pitch and/or volume or a spoken message giving information about the location and proximity of the nearest object. The auditory feedback can be used on its own or in combination with the visual feedback.

Haptic Feedback: Vibration of the joystick to alert the participant to the presence of objects in the vicinity of the powered chair. The strength and frequency of the vibration can be modulated to give some indication of object proximity. This feedback can be combined with the visual data such that the vibration alerts the participant who then inspects the display for additional information.

Reversing Camera: Users have identified reversing as a challenge and requested a reversing camera. This will use the same technology as that in a car. Initially the camera output will be connected directly to a separate display. The visual data will include marker lines to indicate the proximity of any objects and in the future an indication of the chair turning circle.

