3.1 Stage 2 Main Objectives

The main objective is to obtain feedback from the participants on the value and efficacy of the obstacle alerting system. This feedback will be used to inform the ongoing development and specifications for the OAS.

This feedback will be obtained as follows.

Demographic Information: A brief questionnaire will be used to collect demographic information about the participants volunteering to take part in this stage.

Design and Development: Interviews using questionnaires will be conducted before and after the trial to obtain participant input to the specifications for the design and development of an assistive powered wheelchair, with special focus on the obstacle alerting system.

Evaluate Participant Driving Patterns with and without Obstacle Alerting: The impact of the presence of an obstacle alerting system will be investigated. Building on the initial experience from the Stage 1 trial the recorded data will be correlated with the participant's Daily Diary and their feedback on the value of the alerting system.

Typical parameters will be the frequency of use of the chair, the number of collisions, the participant's selection of feedback options and their satisfaction with those options.

For example the measurement of frequency of use of powered chairs and the speeds at which chairs are driven has been investigated by Cooper et al³⁴. This research focused on usage patterns rather than on how the user was driving the PWC. However, even knowledge of the environment in which the chair is driven, the way in which a chair is driven and the frequency with which it is driven can inform the clinician whether the user is confident in driving the chair. Lack of confidence and/or increased number of collisions can arise because the chair has not been set up to match the user's driving ability and/or that the user requires some driving assistance to mitigate these difficulties.

Monitoring driving patterns with and without the obstacle alerting system could provide evidence of the efficacy of that system. In turn this will help to develop a system that will help to improve user confidence and their level of independent mobility and quality of life.

Therefore the goal of Stage 2 is to use participant feedback to help develop a configurable obstacle alerting system which will help improve user independent mobility by enhancing their confidence and safety in driving a powered wheelchair.

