4.7.6.3 Data Recording

The participant will have the choice of which study protocol they wish to follow. Data will be recorded with the OAS feedback turned off and turned on.

This allows the collection of comparative data on how the obstacle alerting system may influence and affect aspects of driving, including confidence in different environments.

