4.9.2 Driving Data Analysis

The recorded data will be analysed to examine the correlations between:

- Time and Date
- Joystick Movement Smoothness²⁶⁻²⁸
- Joystick Displacement patterns
- PWC collisions
- Time spent driving the chair
- Use of Actuators
- Location of the chair

- Daily Diary information [4.8.3]

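### Could the joystick vibration alert distort the joystick smoothness measure when the alerting system is on?

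*Protocol*

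**What the plan says.** The haptic option in section 2.2.5 acts on the control that the participant is steering with: "Vibration of the joystick to alert the participant to the presence of objects in the vicinity of the powered chair". It is not a constant signal: "The strength and frequency of the vibration can be modulated to give some indication of object proximity". Under section 4.8.5.3, participants learn to switch each feedback mode on and off, and may change their settings during the trial.

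Joystick behaviour is also an outcome. Section 4.9.2 lists "Joystick Movement Smoothness". The synopsis gives two related evaluation criteria: "Comparative analysis of driving patterns with and without the obstacle alerting system" and "Analysis of driving patterns through smoothness movement, joystick deflection, positional mapping and daily usage". Section 3.1 adds that "Monitoring driving patterns with and without the obstacle alerting system could provide evidence of the efficacy of that system", and section 4.7.6.3 supplies the two conditions: "Data will be recorded with the OAS feedback turned off and turned on".

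On recording, section 2.2.1 says that the Data Management Unit controls the haptic feedback. It then lists what the unit can record: time and date, joystick movements, user profiles, actuator use, active controller, GPS, inertial data and processed sensor data. Haptic state is not on that list. Section 2.2.4 makes the tablet the place where feedback options are set, without saying whether settings are logged. Section 3.1 names the participant's "selection of feedback options and their satisfaction with those options" among its typical parameters.

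**The concern.** The intervention may act physically on the instrument that measures its effect. Vibration can occur only when feedback is on, haptic is enabled and an object is within sensing range, which section 2.2.3 puts at 2 metres. A ripple leaking into the joystick signal would therefore not cancel in an on/off contrast, and neither more runs nor more participants would average it out. It would make driving look less smooth with the system on, which could hide a benefit or suggest a harm.

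The absence of a stated haptic log seems to make this worse. Processed sensor data would show when objects were near, but not which mode was in use after a participant changed settings part-way. An analysis plan written later cannot recover a field that was never recorded.

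**Working it through.** The protocol gives no figure to reproduce: no ripple size, sampling rate, filter or smoothness formula. The check is first textual, then an illustration on assumed inputs.

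**What must hold for the result to be wrong**

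1. Smoothness is compared on versus off. No section says this outright. It follows from reading the two synopsis criteria with sections 3.1, 4.7.6.3 and 4.9.2; section 4.9.2 itself speaks of correlations. The reading is fair.
2. The participant uses haptic feedback. It is optional.
3. Vibration reaches the recorded joystick signal. The protocol neither shows nor excludes this.
4. The smoothness measure is sensitive to a small, fast ripple. The measure is not specified.
5. The analyst does nothing about it. The protocol does not commit to unfiltered data.

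**How much step 4 matters**

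Assumptions: voluntary movement of amplitude A = 30% of full deflection at F = 1 Hz; ripple amplitude a at frequency f; haptic active for p = 10% of on-time; sinusoids that add in power; no background vibration.

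- Ripple relative to movement: r = (a/A)(f/F)^k, with k = 3 for jerk and k = 1 for velocity.
- On/off ratio of the RMS measure: √(1 + p·r²).

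Jerk with a = 0.1%:

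| f | r | Ratio, unfiltered |
|---|---|---|
| 5 Hz | (0.001/0.3)·125 = 0.417 | √(1 + 0.1·0.174) = 1.009 |
| 10 Hz | (0.001/0.3)·1000 = 3.33 | √(1 + 0.1·11.1) = 1.45 |
| 20 Hz | (0.001/0.3)·8000 = 26.7 | √(1 + 0.1·711) = 8.5 |

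Velocity at 20 Hz: r = (0.001/0.3)·20 = 0.067, ratio 1.0002. With 1% ripple, r = 0.667 and the ratio is 1.02.

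Background vibration present in both conditions shrinks the jerk ratios. Background of 0.3% at 10 Hz adds B = [(0.003/0.3)·1000]² = 100 to both sides. The 20 Hz ratio becomes √((101 + 71.1)/101) = 1.31, and the 10 Hz ratio √((101 + 1.11)/101) = 1.006.

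**How much step 5 matters**

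Apply one filter to on and off data alike: fourth-order low-pass at 4 Hz, run forwards and backwards (an assumed choice). Its gain is 1/(1 + (f/4)⁸), practically 1 at 1 Hz.

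| f | Gain | Filtered r (0.1% ripple) | Ratio |
|---|---|---|---|
| 5 Hz | 1/(1 + 5.96) = 0.144 | 0.060 | √(1 + 0.1·0.0036) = 1.0002 |
| 10 Hz | 1/(1 + 1526) = 0.00066 | 0.0022 | 1.0000 |
| 20 Hz | 1/(1 + 390,625) = 0.0000026 | 0.00007 | 1.0000 |

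For 1% ripple the worst case is at 5 Hz: r = 4.17·0.144 = 0.60, ratio √(1 + 0.1·0.36) = 1.018.

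The filter uses no information about when the vibration was active. The missing log is therefore not what stands between the analyst and a sound comparison.

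**The case for a change.** The strongest case for acting is that leakage would be one-sided, a log is cheap, and it would also serve the option-selection parameter in section 3.1. A filter has limits too. If the sampling rate is too low for the vibration frequency, the ripple folds down into the band of voluntary movement and cannot be filtered out. Filtering may also remove some genuine fast joystick movement. Section 4.9.3 carries the analysis software forward to trials in wheelchair users, so an unnoticed artefact could travel with it.

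Part of this stands. The possible route of contamination is real, and mode after a mid-trial change could not be reconstructed from sensor data alone. The rest is weaker. A log would not cure aliasing; it would only mark the affected periods. Dropping those periods from the on data alone would bring in another bias, because the off data would keep their near-obstacle driving. Any loss of fast movement from filtering applies to both conditions. The protocol does not exclude a log: section 2.2.1 describes what the unit can record, the tablet that sets the options may hold their history, and section 3.1 implies that mode is captured in some form. Log fields and signal conditioning are details that a technical specification or analysis plan ordinarily settles.

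**Conclusion.** No change to the protocol follows. This is a gap in detail that analysts can fill sensibly, not a wrong or contradictory statement. Following the protocol as written is not shown to give a wrong result: it does not say that vibration enters the joystick record, and it fixes neither a sensitive smoothness measure nor unfiltered processing.

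The size is unknown and may be nil. The ratios from 1.00 to 8.5 rest wholly on assumed movement, ripple, duty cycle and frequency. They show only that the answer depends on the measure and the processing, and should not be read as estimates. Within the assumed 5 to 20 Hz range, identical filtering leaves at most 1.0002 for 0.1% ripple and 1.018 for 1% ripple. This assumes sampling fast enough to avoid aliasing, and the residual grows as the vibration frequency nears the filter's cut-off.

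What is at stake is one driving measure in a preliminary evaluation of 10 people whose main goal, under sections 3.1 and 4.9.1, is participant feedback. A team that keeps a timed record of feedback mode, or looks at a short joystick recording with haptic off and on, would be doing sensible engineering; the plan does not depend on it.
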